8.5.2 Safety Analysis Population

The All Subjects as Treated (ASaT) population will be used for the analysis of safety data in this study. The ASaT population consists of all randomized subjects who received at least 1 dose of trial medication. Subjects will be included in the treatment group corresponding to the trial medication they actually received for the analysis of safety data using the ASaT population. For most subjects this will be the treatment group to which they are randomized. Subjects who take incorrect trial medication for the entire treatment period will be included in the treatment group corresponding to the trial medication actually received.

At least 1 laboratory or vital sign measurement obtained subsequent to at least 1 dose of trial medication is required for inclusion in the analysis of each specific parameter. To assess change from baseline, a baseline measurement is also required.

8.6 Statistical Methods

Statistical testing and inference for efficacy analyses is described in Section 8.6.1 and in Section 8.6.2 for safety analyses. Efficacy results that will be considered to be statistically significant after consideration of the strategy for controlling the Type I error are described in Section 8.8, Multiplicity. Nominal p-values may be computed for other efficacy analyses as a measure of the strength of the evidence of a treatment effect for an endpoint rather than a formal test of hypothesis. Unless otherwise stated, all statistical tests will be conducted at the 5% level of significance (2-sided). All p-values will be displayed to 3 decimal places.

All evaluations of suvorexant (with the exception of selected exploratory analyses) will be conducted without distinguishing the dose of suvorexant received (ie, 10 mg or 20 mg).

8.6.1 Statistical Methods for Efficacy Analysis

An analysis of covariance (ANCOVA) using a general linear model for change from baseline in TST at Week 4 with terms for baseline value, baseline severity category (MMSE score of 12 to 20, 21 to 26), age category (non-elderly, elderly), gender, region, and treatment, will be used to evaluate the primary hypothesis. The significance of the difference between suvorexant and placebo in least squares means for TST will be evaluated using an appropriate contrast of model parameters. Sensitivity analyses using this ANCOVA model in conjunction with multiple imputation (MI) to estimate the missing data and measurements collected following discontinuation of trial medication (if available) will also be performed. Details regarding the sensitivity analyses will be provided in the sSAP. The same ANCOVA model will be used to evaluate change from baseline in WASO at Week 4 according to the multiplicity testing strategy as described in Section 8.8. Statistical methods for the analysis of exploratory endpoints will be detailed in the sSAP.

Table 7 summarizes key efficacy analyses.

Table 7 Analysis Strategy for Key Efficacy Variables

Endpoint/Variable (Description, Timepoint)	Statistical Method	Analysis Population	Missing Data Approach
Primary:			
TST – Change from baseline at Week 4	ANCOVA†	Full Analysis set	Primary: Observed data
			Sensitivity: Multiple Imputation (Tipping Point)
Secondary:			
WASO – Change from baseline at Week 4	ANCOVA†	Full Analysis set	Primary: Observed data
			Sensitivity: Multiple Imputation (Tipping Point)
†ANCOVA model with terms for baseline value, baseline severity category (MMSE score of 12 to 20, 21 to 26), age category (nonelderly, elderly), gender, region, and treatment. ANCOVA = Analysis of Covariance Observed data = data observed during Treatment Phase which does not include data collected following discontinuation of trial medication			

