15. Have a TST ≤ 6.5 hours as determined by the Visit 2 Screening PSG confirmed by the central PSG rating vendor.

Visit 3: Baseline PSG Inclusion

Note: Continue to fulfill relevant Inclusion Criteria at Visit 1.

16. Have a mean TST <6 hours on the combined Screening (Visit 2) and Baseline (Visit 3) PSGs, where neither night is >6.5 hours as confirmed by the central PSG rating vendor.

Visit 4: Randomization Inclusion

Note: Continue to fulfill relevant Inclusion Criteria at Visit 1.

17. Have a trial partner who is $\geq 70\%$ compliant with completing the e-diary during the Run-in Period (eg, the last 10 available days of e-diary data from Visit 4).
18. Have $\geq 75\%$ trial medication compliance rate for trial medication taken from Visit 2 to Visit 4. This should be assessed with a standard pill count (ie, number of pills taken divided by (/) number of nights from Visit 2 (inclusive) to the day prior to Visit 4).

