5.2 Trial Treatment(s)

The treatments to be used in this trial are outlined below in [Table 2](#).

Table 2 Trial Treatments

Drug	Dose/ Potency	Dose Frequency	Route of Administration	Regimen/T reatment Period	Use
Single-Blind Placebo Run-in Period					
Placebo (to match suvorexant 10 mg)	0 mg tablet	1 tablet every night	Oral	Nightly for 2 weeks	Placebo
Double-Blind Treatment Period					
Suvorexant 10 mg	10 mg tablet	1 tablet every night	Oral	Nightly for 4 weeks	Investigational
Placebo (to match suvorexant 10 mg)	0 mg tablet	1 tablet every night	Oral	Nightly for 4 weeks	Placebo
*Options for dose escalation (per investigator's discretion) – beginning at Visit 5					
Suvorexant 20 mg*	20 mg tablet	1 tablet every night	Oral	Nightly for 2 weeks	Investigational
Placebo (to match suvorexant 20 mg) *	0 mg tablet	1 tablet every night	Oral	Nightly for 2 weeks	Placebo
*At Visit 5, the dose of suvorexant may be increased to 20 mg (or matching placebo). See Section 5.2.1.2.					

The first dose of trial medication for the single-blind placebo Run-in Period will begin the night of Visit 2; dosing will continue until the subject returns for randomization at Visit 4.

The first dose of trial medication for the randomized double-blind Treatment Period will begin the night of Visit 4. Subjects will remain on the specified trial medication that they are randomized to (suvorexant or matching placebo) throughout the trial, with their last dose on the night of Visit 6. At Visit 5, the investigator may increase the subject's trial medication dose for the remaining 2 weeks. Please see Section 5.2.1.2 for more information.

To maintain blinding with respect to the treatment period (ie, Run-in, Treatment), subjects will not be informed when transitioning between the treatment periods.

The investigator shall take responsibility for and shall take all steps to maintain appropriate records and ensure appropriate supply, storage, handling, distribution and usage of trial treatments in accordance with the protocol and any applicable laws and regulations.

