5.2.2 Timing of Dose Administration

For at-home dosing, subjects are to be instructed (and reminded) to take their trial medication within 30 minutes prior to bedtime. The trial partner is responsible for providing and witnessing daily dosing of trial medication to the subject, and may assist in administration of trial medication if needed. During PSG visits in the sleep lab, trial medication will be administered within 30 minutes before bedtime (Lights Off), and dosing will be witnessed by study personnel.

Each morning, the trial partner will record the dosing time from the previous night, in the e-diary, along with the responses to other e-diary questions.

If a subject happens to miss their evening dose, they should resume taking their medication the following night. The subject should not take an additional dose (ie, the morning following the missed dose) to 'make up' the missed dose. Missed doses should be reported to the site.

It is important that subjects have taken trial medication for at least 3 days prior to a PSG visit (with the exception of Visit 2); therefore, in the event trial medication is interrupted on nights leading up to the end-of-treatment PSG visit (ie, Visit 6), the visit should be rescheduled.

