7.1.2.2.14 Polysomnography (PSG)

7.1.2.2.14.1 PSG Definitions and Scoring

A polysomnogram consists of an electroencephalogram (EEG) for registration of brain activity during sleep, an electro-oculogram (EOG) for registration of the eye movements during sleep, and an electromyogram (EMG) for recording chin muscle activity during sleep. Sleep stage scoring will be performed in 30-second epochs according to the American Academy of Sleep Medicine Manual for the Scoring of Sleep and Associated Events [36]. The data will be captured electronically, in order to permit subsequent spectral analysis. PSG data will be scored by a centralized PSG reading center. Screening and baseline PSG results will initially be reviewed by qualified site scorers, prior to sending to the centralized PSG reading center for confirmation of subject eligibility.

7.1.2.2.14.2 PSG Measurements

Efficacy measures used in this study will be completed as indicated below.

a. PSG Recording and Evaluation Procedures

The central PSG vendor for the trial will provide a standard operating procedure (SOP) detailing how screening and other PSG sessions will be conducted. The SOP will address what types of recordings will be made (eg, the EEG electrode montages, EMG electrodes, cardiac electrodes, plethysmography (strain gauges) to assess respiratory effort) or other recordings to be specified in the SOP. Thus, the definitive set of recordings to be conducted during a PSG screening session will be specified in the SOP, and the SOP will detail which of the recordings will be used on subsequent PSG recording nights.

b. Bedtime and Timing of PSG (Lights-Off and Lights-On)

The time of bedtime in the lab should approximate the subject's bedtime at home (median habitual bedtime), where "bedtime" is defined as the time when the subject intends/attempt to fall asleep, eg, lying down or reclining with eyes closed. The environment should be conducive for sleep (ie, a darkened room, a relatively quiet room, a room free from distractions).

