The Lights-Off time for Visit 2 Screening PSG is defined as approximately ± 10 minutes of the subject's reported median habitual bedtime based on approximately 4 or more days of e-diary data accumulated up to Visit 2-PSG. The Lights-Off time for Visit 3 Baseline PSG is defined as approximately ± 10 minutes of the subject's reported median habitual bedtime based on the last 14 available days of e-diary data leading up to Visit 3. The median habitual bedtime for both Visits 2 and 3 will be calculated by the e-diary and displayed via the vendor e-diary reports.

The Lights-Off time at Visit 6 will be based on the subject's habitual sleep time determined at Visit 3.

The entire PSG recording period from Lights-Off to Lights-On will be 8 hours. Immediately prior to the Lights-Off time, the subject gets into bed, room lights are turned off (ie, the room is dark), and the technician exits the room. The Lights-Off time marks the initiation of the PSG recording period. Lights-Off time must be indicated on the technician's log.

For the timing of electrode calibrations and other PSG activities, refer to the central vendor PSG SOP.

7.1.2.2.14.3 Alcohol Breathalyzer

An alcohol breath test will be performed as specified in the Trial Flow Chart. Subjects should have a negative alcohol breath test on the PSG visit nights. If a subject has a positive alcohol breath test, the test may be repeated at the investigator's discretion and the repeat test must be negative prior to conducting the PSG recording session. If the repeat test continues to be positive, the investigator should determine if the subject should be excluded (Visits 2, 3) or discontinued (Visit 6) from the trial or the PSG visit should be rescheduled. If the decision is to reschedule the PSG, this PSG should take place no sooner than 24 hours and no later than 48 hours. A breathalyzer will be provided to each site by the Sponsor.

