Statistical Methods for Key Efficacy Analyses	The primary hypothesis will be evaluated by comparing suvorexant and placebo with respect to change from baseline in PSG-derived total sleep time (TST) in minutes, at Week 4. Analysis of covariance (ANCOVA) using a general linear model for change from baseline in TST at Week 4, with terms for baseline TST value, baseline severity category (MMSE score of 12 to 20, 21 to 26), age category (non-elderly, elderly), gender, region, and treatment, will be used to evaluate the primary hypothesis. The significance of the difference between suvorexant and placebo in least squares means for change from baseline in TST will be evaluated using an appropriate contrast of model parameters, and according to the multiplicity testing strategy described below.
Statistical Methods for Key Safety Analyses	Program specific pre-specified adverse events of clinical interest (ECIs) will be assessed as Tier 1 events in this study. Estimates of the difference between treatments in the percentage of subjects with these events, 95% confidence intervals, and p-values, will be computed for these Tier 1 events. Tier 2 events are those events for which treatment differences and 95% confidence intervals (but not p-values) will be provided. Tier 3 safety parameters are those for which only descriptive statistics for treatment differences will be provided. Tier 1, 2 and 3

	safety parameters are summarized in Table 8 of Section 8.6.2, Statistical Methods for Safety Analysis.
Interim Analyses	No interim analysis for efficacy or safety is planned for this study.
Multiplicity	Statistical significance for the primary and secondary efficacy hypotheses will be based on a fixed sequential multiplicity strategy to control the overall Type I error at the two-sided 5% significance level. If the comparison of the primary endpoint between treatments is significant at the 5% significance level, then the comparison of the secondary endpoint between treatments will be evaluated at the 5% level of significance.

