8.4.3 Derivations of Efficacy Endpoints

PSG Data

Sleep stage scoring of the PSG recordings will be performed for each 30-second epoch according to the 2007 American Academy of Sleep Medicine (AASM) scoring conventions by a central sleep scoring laboratory. Each 30-second epoch will be scored as wake, Stage N1, N2, N3 or R. For example, TST is defined as the sum of Stages N1+N2+N3+R (in minutes) and WASO is defined as the sum of all wake epochs beginning from persistent sleep (ie, the first epoch of 20 consecutive epochs of Stage N1, N2, N3 or R sleep) to lights on (in minutes). The primary and exploratory PSG endpoints for analysis will be derived by the central sleep scoring laboratory from this information according to pre-specified PSG endpoint definitions contained in a PSG endpoint definition document. The day range for PSG analysis endpoints is defined as follows: Week 4 (+/-7 days from the target Day 30).

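### The TST and WASO models adjust for one baseline PSG; adding the Visit 2 placebo-night PSG as a second covariate is an optional, small gain in precision

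*Combined protocol and SAP*

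**What the plan says.** Section 8.6.1 specifies an ANCOVA, a "general linear model for change from baseline in TST at Week 4 with terms for baseline value", with MMSE category, age category, gender, region and treatment as the other terms. The Section 8.1 summary gives the same model, "with terms for baseline TST value, baseline severity category" and so on. The Table 7 footnote repeats it, and WASO uses it too. Each version has a single PSG covariate.

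Section 8 does not say which PSG is baseline. It leaves PSG derivations to "pre-specified PSG endpoint definitions contained in a PSG endpoint definition document", which is a separate document. Elsewhere the protocol consistently calls Visit 2 the Screening PSG and Visit 3 the Baseline PSG. Flow chart footnote c ties baseline values to Visit 4, but no PSG is done at that visit.

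Inclusion criterion 16 needs both nights: "Have a mean TST <6 hours on the combined Screening (Visit 2) and Baseline (Visit 3) PSGs". Visit 2 is an 8-hour, centrally confirmed recording, and it is already a placebo night: "The first dose of trial medication for the single-blind placebo Run-in Period will begin the night of Visit 2" (Section 5.2). Section 7.1.5.1.2 gives its purpose as eligibility and the detection of other disorders.

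**The concern.** Visit 2 is a second pre-randomization measurement of the endpoint itself, made on placebo, and it should exist for every randomized subject. One night of PSG is a noisy measure of a subject's usual sleep, so a second night can explain some of the Week 4 variation that the first leaves unexplained. Because it precedes randomization, adjusting for it does not change the treatment contrast or threaten the validity of the test.

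What is at stake is precision. The gain is small at the planned 30-minute TST difference. It is larger at the smaller effects the plan also considers (25 minutes for TST, 20 minutes for WASO) and for the chance that both tests in the fixed sequence succeed.

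**Working it through.** **Inputs from Sections 8.6.1 and 8.9.** 117 evaluable per arm (130 × 0.9); SD of change 68 (TST) and 58 (WASO); two-sided 5% t-test; correlation between TST and WASO −0.77.

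**Assumed, because the documents give no figure.** Night-to-night correlation r = 0.3, 0.5 or 0.7; unselected TST mean 300–340 and SD 60–90 minutes.

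**1. The plan's own figures.** The SE of the TST difference is 68 × √(2/117) = 8.89. For 30 minutes, 30/8.89 = 3.37 and 3.37 − 1.96 = 1.41, which gives 92.1% (91.9% by noncentral t; plan 92%). For 25 minutes the t result is 80.0% (plan 80%). WASO gives 90.7% at 25 minutes and 74.7% at 20 (plan 91% and 75%). Joint power is 87.4% by normal approximation (plan 87%). These use the SD of change and credit no covariate, so they do not depend on this point.

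**2. Closed form, before entry selection.** Let r be the correlation of Visit 3 with Week 4 and of Visit 2 with Visit 3, and let r₂ be that of Visit 2 with Week 4. Adding Visit 2 cuts the residual variance by the fraction (r₂ − r²)² / (1 − r²)².

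| | r = 0.3 | r = 0.5 | r = 0.7 |
|---|---|---|---|
| r₂ = r | 5.3% | 11.1% | 17.0% |
| r₂ = r − 0.1 | 1.5% | 4.0% | 4.7% |
| r₂ = r − 0.2 | 0.0% | 0.4% | 0.0% |

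Example at r = r₂ = 0.5. The residual SD with Visit 3 alone is 68 × √((1 + 0.5)/2) = 58.9; with both nights it is 58.9 × √0.889 = 55.5. The 95% half-width goes from 1.96 × 58.9 × √(2/117) = 15.1 minutes to 14.2. Power goes from 97.3% to 98.4% at 30 minutes and from 89.9% to 92.9% at 25.

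**3. With the entry rules applied** (each night ≤390 minutes, mean <360), large-sample simulation, SD of change held at 68 and 58, r₂ = r. Power rows are gains in percentage points, Visit 3 alone against Visit 3 plus Visit 2.

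| | r = 0.3 | r = 0.5 | r = 0.7 |
|---|---|---|---|
| TST residual variance cut | 3.0–4.3% | 7.1–9.3% | 12.9–15.2% |
| TST interval narrower by | 1.5–2.2% | 3.6–4.8% | 6.7–7.9% |
| TST power, 30 min | 0.4 | 1.0–1.2 | 2.1–2.4 |
| TST power, 25 min | 0.9–1.1 | 2.3–2.7 | 4.4–5.1 |
| WASO residual variance cut | 3.9–4.7% | 9.0–10.0% | 15.0–16.0% |
| WASO power, 25 min | 0.4–0.5 | 1.3–1.4 | 2.7–2.8 |
| WASO power, 20 min | 1.2–1.4 | 3.2–3.5 | 5.8–6.2 |

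If r₂ is 0.1 lower, the variance cut is 0.8–4.3% and TST power gains 0.1–0.8 points at 30 minutes and 0.2–1.4 at 25. If r₂ is 0.2 lower, the large-sample cut is at most 0.4%.

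**4. Finite samples.** 20,000 simulated trials of 234 subjects per setting; mean 320; unselected SD 61, 71 and 90 for r = 0.3, 0.5 and 0.7; MMSE, age, gender and region terms omitted. Type I error is 4.6–5.1% under both models. Entries are power in %, Visit 3 alone → with Visit 2.

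| | r = 0.3 | r = 0.5 | r = 0.7 |
|---|---|---|---|
| TST 30 min | 97.6 → 97.9 | 96.6 → 97.5 | 94.9 → 97.3 |
| TST 25 min | 90.7 → 91.6 | 88.2 → 90.6 | 85.1 → 89.7 |
| Both tests, TST 30 and WASO 25 | 96.1 → 96.6 | 94.2 → 95.9 | 91.6 → 95.4 |
| Both tests, TST 25 and WASO 20 | 84.4 → 86.1 | 80.2 → 84.0 | 75.5 → 82.4 |
| Both (30, 25), r₂ 0.1 lower | 96.1 → 96.1 | 93.6 → 94.2 | 91.2 → 92.3 |
| Both (30, 25), r₂ 0.2 lower | 95.9 → 95.8 | 93.3 → 93.2 | 90.8 → 90.6 |

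In the last case the TST residual variance rises 0.2–0.5%, about one subject in 234, and TST power changes by 0 to −0.2 points.

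**The case against.** **Baseline may already include Visit 2.** The separate PSG endpoint document could define baseline as the mean of Visits 2 and 3, as criterion 16 does for entry. Visit 2 would then be in the model, and with equal correlations the mean captures the whole gain. This stands as a condition on the point. It does not make the edit harmful: with both nights as covariates, the treatment estimate is the same whichever change score is used.

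**Visit 2 may predict Week 4 less well.** It is the first placebo night, it is further from Week 4, and Section 5.2.2 exempts it from the requirement of 3 prior days on medication. Its Lights-Off time follows a "median habitual bedtime based on approximately 4 or more days of e-diary data accumulated up to Visit 2-PSG", against the last 14 available days for Visit 3. On the montage, "the SOP will detail which of the recordings will be used on subsequent PSG recording nights", so later nights may be recorded differently. This stands, and it is why the unequal-correlation results matter as much as the equal ones.

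**Little is at stake at the design effect.** With Visit 3 alone, simulated TST power at 30 minutes is already 94.9–97.6%. Gains of 4 to 6 points on a single test need r = 0.7, equal correlations and effects below the design values. This also stands.

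**The large-sample grid is not fully coherent.** SD and r together determine the SD of change, so holding 68 throughout mixes incompatible settings. Matching 68 at r = 0.7 needs an unselected TST SD near 90 minutes within an 8-hour recording. That makes the top of the range less plausible, but the percentage variance cuts hardly move (about 13.6% at SD 90 and 14.6% at SD 60), and the finite-sample runs use matched SDs.

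**Conclusion.** The point holds as an optional refinement. The planned ANCOVA is valid, its stated powers are correct, and the trial stands without the change. On the natural reading that Visit 3 is baseline, a pre-randomization placebo-night measurement of each endpoint goes unused in the efficacy model.

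Using it would cut TST residual variance by about 3–15% if both nights predict Week 4 equally well (r from 0.3 to 0.7), by about 1–4% if Visit 2's correlation is 0.1 lower, and by essentially nothing if it is 0.2 lower. The worst case examined costs about one degree of freedom. All of this rests on assumed night-to-night correlations and on normally distributed TST and WASO.

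**What to change.** In Sections 8.1 and 8.6.1 and the Table 7 footnote, name change from Visit 3 as the response and Visit 3 as the baseline covariate. Add the Visit 2 value of the same endpoint (TST or WASO) as a second continuous covariate, fixed before unblinding. Two rules should go with it:

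- **Re-screened subjects.** State which Visit 2 PSG counts for subjects re-screened under exclusion criterion 33. The protocol leaves that schedule to a Sponsor Communication Form.
- **Missing Visit 2 value.** Keep the subject in the model and impute the value from pre-randomization data pooled over arms. This should be rare, since criteria 15 and 16 require the recording.

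The multiple-imputation sensitivity analyses use the same ANCOVA, so they take on the covariate without further text.

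The cost is one model degree of freedom and no new data. Section 8.0 requires a protocol amendment for a change to primary or key secondary methods, and IRB/ERC approval applies if the change counts as significant. It is best combined with another amendment. If none is wanted, the model can stay as planned; a supportive two-covariate analysis could still go in the sSAP, which Section 8.0 allows for non-confirmatory analyses.
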